16.7 MISSING DATE INFORMATION FOR PRIOR OR CONCOMITANT MEDICATIONS

For prior or concomitant medications, including washout and IOP-lowering medications, incomplete (ie, partly missing) start dates and/or stop dates will be imputed. When the start date and the stop date are both incomplete for a patient, the start date will be imputed first.

16.7.1 Incomplete Start Date

The following rules will be applied to impute the missing numeric fields for an incomplete prior or concomitant medication start date unless the start date > 1 year is marked. If the stop date is complete (or imputed) and the imputed start date is after the stop date, the start date will be imputed using the stop date. If in the cases that the start date > 1 year is marked, the same month and day of the first dose of study treatment and the previous year of the first dose of study treatment will be assigned to the missing fields.

Missing Month and Day

- If the year of the incomplete start date is the same as the year of the first dose of study treatment, the month and day of the first dose of study treatment will be assigned to the missing fields.
- If the year of the incomplete start date is before the year of the first dose of study treatment, *December 31* will be assigned to the missing fields.
- If the year of the incomplete start date is after the year of the first dose of study treatment, *January 1* will be assigned to the missing fields.

Missing Month Only

- If only the month is missing, the day will be treated as missing and both the month and the day will be replaced according to the above procedure.

Missing Day Only

- If the month and year of the incomplete start date are the same as the month and year of the first dose of study treatment, the day of the first dose of study treatment will be assigned to the missing day.
- If either the year of the incomplete start date is before the year of the date of the first dose of study treatment or if both years are the same but the month of the incomplete start date is before the month of the date of the first dose of study treatment, the last day of the month will be assigned to the missing day.
- If either the year of the incomplete start date is after the year of the date of the first dose of study treatment or if both years are the same but the month of the incomplete start date is after the month of the date of the first dose of study treatment, the first day of the month will be assigned to the missing day.

16.7.2 Incomplete Stop Date

The following rules will be applied to impute the missing numeric fields for an incomplete prior or concomitant medication stop date unless the stop date is marked as ongoing. If the imputed stop date is before the start date (imputed or nonimputed start date), the imputed stop date will be equal to the start date. If the stop date is marked as ongoing, the study exit date will be assigned to the missing fields. If the study exit date is not available, the last visit date will be used for imputation.

Missing Month and Day

- If the year of the incomplete stop date is the same as the year of the study exit date, the month and day of the study exit date will be assigned to the missing fields.
- If the year of the incomplete stop date is before the year of the study exit date, *December 31* will be assigned to the missing fields.
- If the year of the incomplete stop date is after the year of the study exit date, *January 1* will be assigned to the missing fields.

Missing Month Only

- If only the month is missing, the day will be treated as missing and both the month and the day will be replaced according to the above procedure.

Missing Day Only

- If the month and year of the incomplete stop date are the same as the month and year of the study exit date, the day of the study exit date will be assigned to the missing day.
- If either the year of the incomplete stop date is before the year of the study exit date or if both years are the same but the month of the incomplete stop date is before the month of the study exit date, the last day of the month will be assigned to the missing day.
- If either the year of the incomplete stop date is after the year of the study exit date or if both years are the same but the month of the incomplete stop date is after the month of the study exit date, the first day of the month will be assigned to the missing day.

17.0 **CHANGES TO ANALYSES SPECIFIED IN PROTOCOL**

Two additional terms the time-matched baseline IOP (either Hour 0 or Hour 2 according to the response variable) and timepoint-by-baseline Hour 0 IOP interaction were added to the primary efficacy analysis model, but were not presented in protocol amendment 2, dated 16MAR2017.

18.0 **REFERENCES**

19.0 **AMENDMENTS**

19.1 **AMENDMENT 1**

[figure not shown]
1. Updated visit schedule tables 4-1 to 4-5 per protocol amd 2.
2. In section 6.3, per-protocol definition is updated to “The per-protocol (PP) population will consist of the subset of patients in the ITT population who 1) had the primary efficacy variable measured; 2) did not have any significant protocol deviations affecting the primary efficacy analyses which include but are not limited to the following:

- violation of key inclusion/exclusion criteria
- wrong or multiple randomization

with no protocol deviations affecting the primary efficacy analyses and IOP measures deemed being influenced by other medications would be excluded from PP analysis, regardless whether the medication constitutes as a protocol deviation. The PP population will be used to confirm the primary efficacy analyses. A separate document to define the key inclusion/exclusion criteria and details of list of patients whose data will be excluded from the PP population analyses will be finalized prior to the Week 12 database lock.”.

3. In section 7.0, updated “The number and percentage of patients in the 3 study populations (ITT, Safety, and PP) will be summarized by treatment group ~~and study center~~; the number of patients screened will be summarized overall only ~~by the study center~~. ”.
4. In section 7.0, deleted “~~Patients screened but not randomized along with the associated reasons for failure to randomize will be tabulated overall for the all screened patients.~~”.
5. In section 7.0, added the study and cycle completer definition “The study completers will be defined as the patients who received at least 1 injection and complete the extended safety follow up visits. The completers for each cycle will be defined as the patients who received injection in the relevant cycle and completed the cycle by either receiving the following injection or completing the extended safety follow up visits.”.
6. In section 10.1, added “The non-study IOP-lowering medication is defined as the medication being specifically marked as “Yes” to the question “Is this Medication used as a non-study IOP-lowering Medication?” on concomitant medication electronic case report from (eCRF).”.

7. In section 10.1.1, updated the primary efficacy analysis model, “The model will include IOP time-matched change from baseline as the response variable and treatment, timepoint (Hours 0 and 2 at each visit of Weeks 2, 6, and 12), treatment-by-timepoint interaction and baseline IOP stratification as fixed effects factors, as well as time-matched baseline IOP (either Hour 0 or Hour 2 according to the response variable) as a covariate and timepoint-by-baseline Hour 0 IOP interaction.”.
8. In section 10.1.1, added “Mis-stratified subjects, if any, will be analyzed based on the stratum to which the subjects should have been randomized.”
9. In section 10.1.1, updated psedudo [REDACTED] code for primary efficacy analysis.
10. In section 10.1.1, sensitivity analyses on primary efficacy variable were updated “At each visit/hour, treatment difference and its 95% confidence interval will be based on least square means by using an Analysis of Covariance (ANCOVA) model with IOP time-matched change from baseline as the response variable, treatment as a factor, and time-matched baseline IOP (either at Hour 0 and baseline IOP at or Hour 2 according to the response variable) as a covariates.”.
11. In section 10.1.1, sensitivity analyses on primary efficacy variable using MI were updated “Step 2: Multiple imputation by treatment group using linear regression with factors of demographics and baseline characteristics including but not limited to race group, sex, and lens status; and age, IOP baseline IOP values at both Hour 0 and Hour 2 as a covariates (defined as the regression step) will be applied to the data obtained from the MCMC step.”.
12. In section 10.1.1, updated psedudo [REDACTED] code for MI.
13. In section 10.2.1, deleted “~~For the superiority test of study eye time-matched IOP change from baseline at each hour of a visit, the null hypothesis is that there is no difference between a given Bimatoprost SR dose strength and timolol. The alternative hypothesis is that there is a difference. The null hypothesis will be tested using the same MMRM model as described for the primary efficacy analysis in Section 10.1.~~”.
14. In section 10.2.1, updated “The A 2-sided 95% confidence interval for the mean difference in study eye time-matched IOP change from baseline between each Bimatoprost SR dose strength and timolol (Bimatoprost SR minus timolol) will be provided-derived in the primary analysis will be used for secondary analysis of superiority comparison.”.
15. In section 10.3.2, deleted “~~The comparison will be made between each Bimatoprost SR dose strength and timolol for study eye IOP at each timepoint (Hours 0 and 2 at Weeks 2, 6, and 12) using the ITT population.~~”.

16. In section 10.3.2, superiority claiming criterion for secondary efficacy analysis for US FDA is updated “Bimatoprost SR 15 µg will be tested for superiority and considered statistically superior to timolol, if it shows statistically significant difference in favor of Bimatoprost SR 15 µg at ~~3 or more~~ all 6 time points ~~and numerically better at the remaining time points of all scheduled timepoints~~ (Hours 0 and 2 at Weeks 2, 6, and 12).”.
17. 
18. 
19. In section 11.0, definition of cycle and safety follow up is added “For all cycle summary analyses, in order to compare cycles of similar duration, the data included in each cycle will be,
- Cycle 1 (16 weeks): data from the 1st injection to the 2nd injection date -1 or upper bound of week 15 visit window (section 16.1) if a patient didn’t receive the 2nd injection;
 - Cycle 2 (16 weeks): data from the 2nd injection to the 3rd injection date -1 or upper bound of week 31 visit window (section 16.1) if a patient didn’t receive the 3rd injection
 - Cycle 3 (20 weeks): data from the 3rd injection to upper bound of week 52 visit window (section 16.1);
 - Safety follow up: data after week 52 for patients with 3 injections and safety follow up.”.
20. In section 11.1, the overall summary of AEs was updated to “Overall summary of AEs will be provided on a per-patient basis for categories of all TEAEs, treatment-related TEAEs, injection procedure-related TEAEs, study drug-related TEAEs, ~~serious adverse events~~ TEAEs (STEAEs), deaths, and AEs leading to study discontinuation.”

21. In section 11.1, TEAE summary table was updated to “the number and percentage of patients reporting TEAEs will be provided on a per-patient basis by 1) SOC and preferred term; 2) SOC, preferred term and severity in descending order of frequency for each treatment group.”.
22. In section 11.1, non-ocular TEAEs summary was updated to “The number and percentage of patients reporting nonocular TEAEs in each treatment group will be tabulated by 1) descending percentage in any group; 2) by SOC, and preferred term and severity; and 3). Also the number and percentage of patients reporting treatment-related by causal relationship to the study treatment (including study drug related or injection procedure related) nonocular TEAEs in each treatment group will be tabulated by SOC and preferred term.
23. In section 11.1, deleted “~~If more than 1 nonocular AE is coded to the same preferred term for the same patient, the patient will be counted only once for that preferred term using the greatest severity and strictest causality for the summarization by severity and causal relationship.~~”.
24. In section 11.1, ocular TEAEs summary was updated to “Similar analyses will be done for ocular TEAEs including 1) by PT and severity; 2) treatment-related TEAEs by PT for each treatment group by study eye and fellow eye. ~~Additionally, ocular TEAEs in each treatment group will also be tabulated by 1) by causal relationship to the study drug; 2) by causal relationship to injection procedure.~~ ”.
25. In section 11.1, serious TEAEs summary was updated to “Nonocular and ocular STEAEs will be summarized by preferred term and treatment group, respectively.”.

26. [REDACTED]

27. [REDACTED]

28. [REDACTED]

29. [REDACTED]

30. [REDACTED]

31. [REDACTED]

32. Deleted section 16.4 MISSING DATE OF THE LAST DOSE OF STUDY TREATMENT, and all following sections were re-numbered. ~~“When the date of the last dose of study treatment is missing for a patient in the safety population, all efforts should be made to obtain the date from the investigator. If after all efforts are made it is still missing, the last available dosing record date will be used as the last dose date.”~~.

33. In section 17.0, updated changes in this amendment to analyses specified in protocol, “There are no major changes to the analyses specified in protocol amendment 1, dated 11AUG2015. Two additional terms the time-matched baseline IOP (either Hour 0 or Hour 2 according to the response variable) and timepoint-by-baseline Hour 0 IOP interaction were added to the primary efficacy analysis model, but were not presented in protocol amendment 2, dated 16MAR2017.”

19.2 AMENDMENT 2

1. In section 6.3, updated “The per-protocol (PP) population will consist of the subset of patients in the ITT population who ~~1) had the primary efficacy variable measured. ; 2) did not have any significant protocol deviations affecting the primary efficacy analyses which include but are not limited to the following:~~

- ~~• violation of key inclusion/exclusion criteria~~
- ~~• wrong or multiple randomization~~

IOP measures deemed being influenced by other medications would be excluded from PP analysis, ~~regardless whether the medication constitute as a protocol deviation.~~ The PP population will be used to confirm the primary efficacy analyses. A separate document to define the key inclusion/exclusion further criteria and details of patients ~~whose data will to~~ be excluded from the PP analyses will be finalized prior to the Week 12 database lock.”

2. In section 6.4, updated “Clinical lab test data and general (non-ophthalmic) physical examination will only be collected at screening and will not be analyzed.”
3. In section 8.0, updated “Prior and concomitant medications will be separately summarized using the safety population for each treatment group as the number and percentage of patients under each indication preferred term (MedDRA) and unique base preferred name from the World Health Organization Drug Dictionary Enhanced (WHODDE).”
4. In section 8.0, added “A non-study IOP-lowering medication is defined as a medication for which the investigator specifically marked “Yes” to the question “Is this medication used as a non-study IOP-lowering medication?” on the concomitant medication electronic case report from (eCRF). A non-study IOP-lowering procedure is defined as a procedure for which the investigator specifically marked “Yes” to the question “Was this an IOP-lowering procedure?” on the concurrent procedure eCRF. Other medications or procedures that could potentially reduce IOP but are not marked in the eCRF as non-study IOP-lowering medications/procedures will be listed in the separate document used to identify data excluded from the PP analysis.”
5. In section 10.1, updated “To avoid confounding of efficacy data, IOP values obtained after initiating the use of non-study IOP-lowering medication or procedure in an eye will be excluded from the calculation of the summary statistics and the statistical analyses for that eye, but raw values will be presented in the listings.”
6. In section 10.1, moved “The non-study IOP-lowering procedure is defined as the procedure being specifically marked as “Yes” to the question “Was this an IOP-lowering procedure?” on concurrent procedure eCRF.” to section 8.0

7. In section 10.1.1, updated the primary efficacy analysis model, “The model will include IOP time-matched change from baseline as the response variable and treatment, timepoint (Hours 0 and 2 at each visit of Weeks 2, 6, and 12), treatment-by-timepoint interaction and baseline IOP stratification as fixed factors, as well as time-matched baseline IOP (either Hour 0 or Hour 2 according to the response variable) as a covariate and timepoint-by-baseline ~~Hour 0~~ time-matched IOP interaction.”

8. In section 10.1.1, updated pseudo [REDACTED] code for primary efficacy analysis.

9. [REDACTED]

10. [REDACTED]

11. [REDACTED]

12. [REDACTED]

[REDACTED]

[REDACTED]

[REDACTED]

[REDACTED]

13. [REDACTED]

14. In section 11.0, updated “Continuous variables will be summarized by number of patients and mean, SD, median, the 1st quartile and the 3rd quartile, minimum, and maximum values.”

15. In section 11.0, updated “Extended safety follow up: data after week 52 for patients with 3 injections and ~~safety~~ extended follow up.”

16. In section 11.1, deleted “~~If more than 1 ocular AE is coded to the same preferred term for the same patient eye, the patient eye will be counted only once for that preferred term using the greatest severity and strictest causality for the summarization by severity and causal relationship.~~”

17. In section 11.1, added “Ocular AEs leading to study drug discontinuation will be summarized by preferred term and treatment for the entire study period and also for each cycle. Ocular AEs leading to study drug discontinuation are defined as the ocular AEs with action regarding study drug reported as “Discontinued” or “Regimen Changed” on the eCRF AE form.”

18. Delete IOP section (originally section 11.3.4), all subsequent section numbers were updated.

19. [REDACTED]

20. [REDACTED]

21. [REDACTED]

22. [REDACTED]

[REDACTED]

[figure not shown]
[REDACTED]

[REDACTED]

[REDACTED]

[REDACTED]

19.3 AMENDMENT 3

1. 
2. In section 11.1, updated “Overall summary of TEAEs will be provided on a per-patient basis for categories of all TEAEs, treatment-related TEAEs, injection procedure-related TEAEs, study drug-related TEAEs, serious TEAEs (STEAEs), deaths, and TEAEs leading to study discontinuation.”
3. In section 11.1, updated “Nonocular TEAEs and ocular TEAEs leading to premature discontinuation of the study will be summarized by preferred term and treatment, respectively. Similarly, ocular TEAEs leading to premature discontinuation will also be tabulated by treatment group by treatment cycle.”
4. In section 11. 1, updated “Ocular TEAEs leading to study drug discontinuation will be summarized by preferred term and treatment for the entire study period and also for each cycle. Ocular TEAEs leading to study drug discontinuation or regimen change are defined as the ocular TEAEs with action regarding study drug reported as “Discontinued” or “Regimen Changed” on the eCRF AE form.”
5. In section 11.1, updated “Ocular TEAEs leading to implant removal will be summarized by preferred term and treatment for the entire study period and also for each cycle.”
6. In section 11.1, updated “Corneal TEAEs and Anterior chamber inflammation TEAEs will be summarized by preferred term and treatment group, respectively. Similar analyses will be done by treatment cycle. The full list of corneal AEs and Anterior chamber inflammation AEs will be provided prior to each database lock. Additional subcategory of TEAEs may be analyzed separately, such as for ocular TEAE associated with use of a prostaglandin analog (PGA), etc.”
7. In section 16.7.2, deleted “~~If the date of the last dose of study treatment is missing, impute it as described in Section 16.4.~~”, updated “If the stop day date is marked as ongoing, the study exit date will be assigned to the missing fields.”, and added “If the study exit date is not available, the last visit date will be used for imputation.”.
8. In section 16.7.2, updated the following,

“Missing Month and Day

• If the year of the incomplete stop date is the same as the year of the ~~last dose of study treatment~~ study exit date, the month and day of the ~~last dose of study treatment~~ study exit date will be assigned to the missing fields.

- If the year of the incomplete stop date is before the year of the ~~last dose of study treatment~~ study exit date, *December 31* will be assigned to the missing fields.
- If the year of the incomplete stop date is after the year of the ~~last dose of study treatment~~ study exit date, *January 1* will be assigned to the missing fields.

Missing Day Only

- If the month and year of the incomplete stop date are the same as the month and year of the ~~last dose of study treatment~~ study exit date, the day of the ~~last dose of study treatment~~ study exit date will be assigned to the missing day.
- If either the year of the incomplete stop date is before the year of the ~~date of the last dose of study treatment~~ study exit date or if both years are the same but the month of the incomplete stop date is before the month of the ~~date of the last dose of study treatment~~ study exit date, the last day of the month will be assigned to the missing day.

ALLERGAN

BIM SR study 192024-091 Statistical Analysis Plan Text_Amd 3

Date (DD/MMM/YYYY)/Time (PT)

Signed by:

Justification

[REDACTED]

[REDACTED]

[REDACTED]

[REDACTED]

[REDACTED]

[REDACTED]

[REDACTED]

[REDACTED]

[REDACTED]

[REDACTED]

[REDACTED]

[REDACTED]

[REDACTED]

[REDACTED]

[REDACTED]

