8.2 Washout Intervals

All patients must provide informed consent prior to beginning any drug washout for the purposes of inclusion in this study. Patients currently being treated with IOP-lowering medication(s) in either eye will begin washout of these medication(s) following completion of the screening procedures. The Screening and Washout periods may not be concurrent. The Washout period will be up to 42 days depending on the minimum washout period schedule below.

If patients cannot discontinue their prescribed therapy for up to 6 weeks to meet the washout period for study entry, the investigator may switch the patient's medication to one that requires a shorter washout interval during the washout of the original medication (Table 8). Nonetheless, the investigator should adhere to the minimum washout period for all IOP-lowering medications as indicated in Table 8.

If, after initial washout, the IOP does not meet entry criteria and the investigator believes this is due to inadequate washout, if time remains in the Washout period, he/she may perform additional washout, as long as the total Washout period does not exceed 42 days.

For patients undergoing a washout, interim safety evaluation(s) of IOP at some time during the washout period may be performed at the discretion of the investigator.

Note: Medications should only be discontinued (washed out) if the investigator feels that it is safe and appropriate, and if the patient is willing to discontinue the medication for the duration of the study. If the medication cannot be discontinued, then the patient will not be eligible for study entry.

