8.0 DEMOGRAPHICS AND OTHER BASELINE CHARACTERISTICS

Continuous variables will be summarized by number of patients and mean, standard deviation (SD), median, minimum, and maximum values. Categorical variables will be summarized by number and percentage of patients.

Demographics

Demographic parameters including age, age group, race, race group, and sex; and baseline characteristics including weight (kg), and height (cm) will be summarized descriptively by treatment group for the ITT population. Patient's age (years) will be classified into categories of less than 45 years, between 45 years and 65 years, inclusive, and greater than 65 years. In addition, race will be further grouped as white versus nonwhite.

Other disease characteristics (for study eye only), including iris color, diagnosis of either OAG (primary OAG, pseudoexfoliation glaucoma, pigmentary glaucoma) or OHT, baseline Hour 0 IOP (≤ 25 mm Hg or > 25 mmHg), iridocorneal angle size, and central endothelial cell density, will be summarized descriptively by treatment group for the ITT population. Study eye iris color will be summarized by color for each of the following categories: monochromic, heterochromic peripupillary, and heterochromic diffuse.

Medical History and Ophthalmic History

Findings in patients' medical histories, and ophthalmic histories, will be coded using the Medical Dictionary for Regulatory Activities. The number and percentage of patients with abnormalities in medical histories (ophthalmic excluded) in each system organ class (SOC) and preferred term will be summarized by treatment group for the safety population.

Abnormalities in ophthalmic history in each system organ class and preferred term will be separately summarized as frequency count and percent by treatment group for study eye and pooled for fellow eye in the safety population.

Surgical and Ophthalmic surgical history will be presented in listings.

Prior and Concomitant Medications/Procedures

Prior medication is defined as any medication taken before the date of the first dose of study treatment. Concomitant medication is defined as any medication taken on or after the date of the first dose of study treatment. If any medication is taken before the date of the first dose of study treatment and continues after initiation of study treatment, it will be considered as both a prior and concomitant medication.

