Prior and concomitant medications will be separately summarized using the safety population for each treatment group as the number and percentage of patients under each indication preferred term (MedDRA) and unique base preferred name from the World Health Organization Drug Dictionary Enhanced (WHODDE).

Concurrent procedures will be provided in the listings.

Non-study IOP Lowering Medications/Procedures

A non-study IOP-lowering medication is defined as a medication for which the investigator specifically marked “Yes” to the question “Is this medication used as a non-study IOP-lowering medication?” on the concomitant medication electronic case report from (eCRF). A non-study IOP-lowering procedure is defined as a procedure for which the investigator specifically marked “Yes” to the question “Was this an IOP-lowering procedure?” on the concurrent procedure eCRF.

Other medications or procedures that could potentially reduce IOP but are not marked in the eCRF as non-study IOP-lowering medications/procedures will be listed in the separate document used to identify data excluded from the PP analysis.

Washout Ocular Medication

Similarly, washout ocular medications will be tabulated by treatment group for the study eye and pooled for the fellow eye.

9.0 **EXTENT OF EXPOSURE AND TREATMENT COMPLIANCE**

9.1 **EXTENT OF EXPOSURE**

Throughout the study, each patient will receive up to 3 administrations of Bimatoprost SR or Sham injection in each eye with a fixed interval of 16 weeks. The number and percentage of patients receiving Bimatoprost SR or Sham treatment in the study eye during the study will be tabulated by the number of treatment administrations for each treatment group.

Each patient's study duration will be calculated as the number of days between the exit date and Day 1 Administration Day, inclusively (date of the exit - Day 1 Administration date + 1). Patients' study duration will be summarized using descriptive statistics for each treatment group.

10.0 **EFFICACY ANALYSES**

The primary efficacy variable for country/regions other than US will be time-matched IOP change from baseline in the study eye. The primary efficacy variable for the United States (US) Food and Drug Administration (FDA) (Division of Transplant and Ophthalmology Products) is IOP in the study eye (Section 10.3.1).

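### Partial stop dates of washout drugs are imputed to the latest possible date with no cap at first dose, so some washed-out drugs can be counted as concomitant

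*SAP*

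**What the plan says.** - **Scope.** SAP 16.7: "For prior or concomitant medications, including washout and IOP-lowering medications, incomplete (ie, partly missing) start dates and/or stop dates will be imputed". Start dates are imputed before stop dates when both are incomplete.
- **Day missing.** SAP 16.7.2: if the recorded stop month "is before the month of the study exit date, the last day of the month will be assigned to the missing day". If it is the exit month, the exit day is used.
- **Month and day missing.** "If the year of the incomplete stop date is before the year of the study exit date", December 31 is used. If the years are the same, "the month and day of the study exit date will be assigned to the missing fields".
- **The only guard.** If the imputed stop falls before the start, "the imputed stop date will be equal to the start date". This is a floor. There is no ceiling at first dose.
- **Classification.** SAP 8.0: "Concomitant medication is defined as any medication taken on or after the date of the first dose of study treatment". A drug that began earlier and continues past first dose is counted as both prior and concomitant.
- **Washout.** Protocol 8.2: "The Washout period will be up to 42 days depending on the minimum washout period schedule below". Entry IOP is judged after washout, and a drug that cannot be discontinued makes the patient ineligible.

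**The concern.** For most concomitant drugs with a partial stop date, it is unknown whether use continued past first dose, so a late imputed date is a cautious choice. For a drug recorded as washed out, this is known: it stopped before Baseline. A stop date on or after Day 1 contradicts the record. The rule names these drugs and makes no exception for them.

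Followed exactly, the rule can list a washed-out glaucoma drug among treatments taken during the study, in a trial whose endpoint is IOP. There is also a possible link to the per-protocol analysis. SAP 6.3 leaves out IOP values judged to be influenced by other medications. Under SAP 8.0, drugs that might lower IOP but were not marked as such on the eCRF "will be listed in the separate document used to identify data excluded from the PP analysis".

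**Working it through.** The plan gives no figure to reproduce. The check applies the rules of 16.7.1 and 16.7.2 to every possible Day 1.

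**Inputs.** The rules are as listed above. Day 1 runs over every date of 2015 to 2018 (1,461 days, 48 months), which assumes a uniform calendar. The true stop is w days before Day 1. The drug-specific washout table in Protocol 8.2 is not shown, so w is taken over a range up to the stated maximum of 42 days.

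**When a stop is moved.** With the day missing, the imputed stop is the month end or the exit day. It falls on or after Day 1 only if the stop and Day 1 share a calendar month. With month and day missing, they must share a calendar year.

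**Day missing.** In a month of length L, a Day 1 has its stop in the same month on L − w dates (none if w ≥ L). For w ≤ 28 the share is (1,461 − 48w)/1,461. At w = 30 only the 28 months of 31 days contribute, one date each.

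**Month and day missing.** The share is (1,461 − 4w)/1,461.

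| Gap w (days) | Day missing | Month and day missing |
|---|---|---|
| 3 | 1,317/1,461 = 90.1% | 1,449/1,461 = 99.2% |
| 5 | 1,221/1,461 = 83.6% | 1,441/1,461 = 98.6% |
| 14 | 789/1,461 = 54.0% | 1,405/1,461 = 96.2% |
| 21 | 453/1,461 = 31.0% | 1,377/1,461 = 94.3% |
| 28 | 117/1,461 = 8.0% | 1,349/1,461 = 92.3% |
| 30 | 28/1,461 = 1.9% | 1,341/1,461 = 91.8% |
| 31 | 0% | 1,337/1,461 = 91.5% |
| 42 | 0% | 1,293/1,461 = 88.5% |

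A direct enumeration gave the same shares. They were identical with the reference date at Day 1 + 14, 84, 224 and 608 days.

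**Example.** Day 1 is 20 May 2016 and exit is 20 January 2018.
- Stop in May 2016, day unknown: imputed 31 May 2016, after Day 1.
- Stop in April 2016, day unknown: imputed 30 April 2016, before Day 1.
- Stop in 2016 only: imputed 31 December 2016, after Day 1.
- Stop in 2015 only: imputed 31 December 2015, before Day 1.

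**Second route, through the floor.** A start recorded only as 2016 is imputed first, to Day 1 (20 May 2016). A stop in April 2016 with day unknown becomes 30 April, and the floor then raises it to 20 May. The drug becomes concomitant although its stop month precedes Day 1. SAP 16.7.1 has a mirror rule that would pull the start back to the stop instead. The order stated in 16.7 leads to the floor, but the two rules can give different answers for the same record.

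**The case against.** Latest-possible imputation is a common cautious convention. Washout runs under the investigator's direction, after consent and screening, so partial stop dates should be few and year-only dates fewer still. SAP 8.0 tabulates washout ocular drugs separately, so these records can be identified. The affected output is descriptive.

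The points on rarity and limited reach stand. The separate table does not answer the point, because nothing in SAP 8.0 removes washout drugs from the concomitant table. Caution is no defence where the record already shows that the drug was stopped.

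Three stronger readings are tempting, and the documents do not support them.
- **Every washed-out drug is moved past first dose.** Complete dates are untouched. With only the day missing, a stop in an earlier month than Day 1 stays before Day 1 unless the floor route applies. A moved drug is usually both prior and concomitant, so it does not leave the prior table.
- **The exit-date anchor is the cause.** The shares do not change with the reference date. The cause is the latest-possible date without a cap.
- **Efficacy data are wrongly removed.** SAP 10.1 excludes IOP after *initiation* of a non-study IOP-lowering medication or procedure, which SAP 8.0 identifies by the investigator's eCRF mark. An imputed stop date triggers neither. The per-protocol criteria sit in a separate document that is not available here, so an effect there is possible but not shown.

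**Conclusion.** The point holds as a minor defect. A stated rule, applied to a class of drugs it names, can give a date that contradicts the protocol's washout requirement and the SAP's own classification. Given a partial stop date with only the day missing, the share affected runs from about 84% at a 5-day gap to 8% at 28 days and zero from 31 days. With only the year known it is 88.5% to 99.2% for gaps of 42 down to 3 days. These shares assume a uniform Day 1 and illustrative gaps. The number of partial washout dates is not given, so the number of patients affected cannot be computed. What is shown is misclassification in the concomitant-medication summaries. The ITT primary analysis is unaffected.

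**What to change.** Add to SAP 16.7.2:

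*For medications recorded as washout, an imputed stop date may not be later than the day before the Baseline visit. For other medications known to have stopped before first dose, it may not be later than the day before first dose. This cap takes precedence over the floor at the start date. An imputed start date later than the capped stop date is set to the capped stop date.*

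Two caps are needed because a non-washout drug may properly have stopped between Baseline and Day 1. If the recorded month or year lies wholly after the cap, the record should be queried. The exit-date anchor can stay.

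The cost is a few SAP sentences and a small change to the date derivation. No new data are needed.
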